8.2. Sample Size Justification

A total of 37 patients will be included in this feasibility study. The physicians are familiar with the AirWaze investigational device in a non-clinical setting. The clinical setting will function as clinical and technical de-risking of the software program and the information from this study will be used to design a robust pivotal claim-driven study. Semi-structured questionnaires will be used to assess the overall system usability and the accuracy of the AirWaze CBCT-FS scan. Furthermore, the number of imaging and algorithm failures and the ability to work around quickly will be evaluated. Taking into account a 10% drop-out rate, it is expected by experts that a Per Protocol population of 33 patients is sufficient to de-risk the AirWaze features.

8.3. General Consideration

All results will be summarized using the following descriptive statistics: n, mean with 95% confidence interval (CI), standard deviation (SD), median, interquartile range (IQR), minimum and maximum. Categorical data will be summarized as the number and percentage of subjects in each category (including the category 'missing' if applicable). Generally, percentages will be calculated for missing categories and all percentages will be based on the total number of subjects in the population (denoted by N on the summary tables and figures). Statistical analysis will be performed using SAS (SAS® Life Science Analytics Framework) and/or R statistical software (<https://www.r-project.org/>).

All data will be listed for the enrolled population. The data will be sorted by subject number.

For summary statistics, the mean and median will be displayed to one decimal place greater than the original value and the measure of variability (e.g., SD) will be displayed to two decimal places greater than the original value. Minimum and maximum will be reported to the same decimal places as the original value. Percentages will be displayed in 1 decimal place. P-values will be reported to three decimal places; p-values less than 0.001 will be reported as $p < 0.001$.

8.4. Subject Disposition

Subject disposition, including the total number of subjects evaluated, will be presented. In addition, a listing will be provided with the reasons why the subject was not evaluated.

8.5. Demographics and Baseline Characteristics

Demographics Subjects

Information on age (years), height (cm), and body mass index (BMI) (kg/m^2) will be reported and summarized as continuous data. Gender (male, female, other), and comorbidities will be reported as categorical data.

Demographics Operators

The experience as a medical specialist (years), and the number of CBCT-guided bronchoscopy procedures performed (n) will be reported and summarized as continuous data.

Baseline Subject Characteristics

Lesion size (mm, long axial axis), and volume (mm^3), will be reported and summarized as continuous data (mean \pm SD). Location (lobe; LUL, LLL, RUL, RML, RLL), nodule aspect (solid, sub-solid, ground glass opacity, cystic), PET FDG avidity (no uptake, faint, moderate, intense) will be reported as categorical data. Overall ROSE pathology outcome at index procedure will be divided into benign, malignant, atypical cells (non-diagnostic) and not representative biopsy samples.

IGT Systems	Feasibility Clinical Investigation Protocol	Doc ID: XCY607-130895
	AirWaze – easy and advanced tools for CBCT guided lung interventions	Rev: 04 Date: 2024-Jun-19 Page 26 of 56

8.6. Primary objective

Objective

The primary objectives of this feasibility clinical investigation are to assess the overall system usability of the Philips AirWaze investigational device (version 1.1) as measured by the System Usability Score (SUS) and the accuracy of the tool-in-lesion confirmation scan CBCT-FluoroSweep compared to the conventional CBCT.

Primary Endpoints

The system usability will be assessed by using the System Usability Scale (SUS)¹⁵. An average SUS of greater than 70 will indicate a good usability design of the AirWaze Software solution. The SUS will be measured per operator every 4 procedures that they have operated the AirWaze software solution.

Image-based tool-in-lesion confirmation accuracy of CBCT-FS is defined as the number of procedures where CBCT-FS scans were adequate to define tool-in-lesion compared to conventional CBCT scans (gold-standard). The accuracy is defined as the sum of the number of tool-in-lesion in both CBCT-FS and CBCT, and the number of no tool-in-lesion confirmation in both CBCT-FS and CBCT, divided by the total number of CBCT-FS and CBCT pairs. Image based tool-in-lesion confirmation accuracy of 90% will indicate that the CBCT-FS is postulated to be sufficient for navigation bronchoscopy.

Analysis

The results will be analyzed by using the average SUS and the SUS score development in time. No statistical test will be performed on the SUS scores due to limited data points. A SUS greater than 70 will indicate a good usability design of the AirWaze software device. More information on the SUS questionnaire can be found in Appendix I: System Usability Scale (SUS).

The results will be analyzed by calculating the overall accuracy of the CBCT-FS for tool-in-lesion confirmation. More information on the CBCT-FS scan questions can be found in Appendix II: CBCT-FS compared to CBCT. An additional analysis will be performed within the tool-in-lesion confirmation group. Tool-in-lesion scans are evaluated and subdivided into center-strike and off-center confirmation scans¹⁸, subsequently the accuracy is calculated.

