Appendix II: CBCT-FS compared to CBCT

CBCT-FluoroSweep

- What is the purpose of the CBCT-FS scan?
 - Confirm tool-in-lesion
 - Determine location of the catheter compared to the lesion
 - Other,
- If confirm tool-in-lesion purpose, can you confirm tool-in-lesion based on the CBCT-FS scan?
 - Yes, there is tool-in-lesion confirmation.
 - No, there is no tool-in-lesion confirmation.
 - Inconclusive, because
- If confirm tool-in-lesion purpose AND tool-in-lesion confirmation, is the tool-in-lesion center-strike or off-center¹⁸?
 - Center-strike
 - Off-center strike
- To what extent is the CBCT-FS imaging useful to reposition or continue (for all purposes)?

Scan	1 Not useful at all	2	3	4	5 Very useful
CBCT-FS					

- Did you notice/experience any artefacts or glitches? If yes, please elaborate.
.....

CBCT (gold-standard imaging)

- What is the purpose of the CBCT scan?
 - Confirm tool-in-lesion
 - Determine location of the catheter compared to the lesion
 - Other,
- If confirm tool-in-lesion purpose, can you confirm tool-in-lesion (in all three orthogonal orientations) based on the CBCT scan?
 - Yes, there is tool-in-lesion confirmation in all three orthogonal orientations.
 - No, there is no tool-in-lesion confirmation.
 - Maybe, the quality of the CBCT scan is not sufficient to determine tool-in-lesion confirmation.
- If confirm tool-in-lesion purpose AND tool-in-lesion confirmation, is the tool-in-lesion center-strike or off-center¹⁸?
 - Center-strike
 - Off-center
 - Lesion is too small to define center-strike or off-center*
- Did the CBCT scan change your plan based on the CBCT-FS?
 - Yes
 - No
- Did you notice/experience any artefacts or glitches? If yes, please elaborate.
.....

* The lesion size is comparable to the catheter size.

IGT Systems	Feasibility Clinical Investigation Protocol	Doc ID: XCY607-130895
	AirWaze – easy and advanced tools for CBCT guided lung interventions	Rev: 04
		Date: 2024-Jun-19
		Page 43 of 56

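### The primary accuracy divides by all scan pairs, but Appendix II leaves some pairs unscored and words the two readings differently, so a perfect CBCT-FS can miss 90%

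*Combined protocol and SAP*

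**What the plan says.** **Formula.** Section 8.6 takes the pairs that are positive on both scans "and the number of no tool-in-lesion confirmation in both CBCT-FS and CBCT, divided by the total number of CBCT-FS and CBCT pairs". Section 7.1.1 gives the same formula. Both then set 90% as the level at which CBCT-FS is postulated to be sufficient. One sentence before the formula, 8.6 describes the endpoint as "defined as the number of procedures where CBCT-FS scans were adequate to define tool-in-lesion compared to conventional CBCT scans (gold-standard", which counts procedures and not pairs.

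**When a pair arises.** Under Section 7.4 a CBCT-FS accompanies a CBCT whenever CBCT is indicated. Appendix VI says the first CBCT is conventional and the CBCT-FS is added to later scans.

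**What is scored.** Appendix II records a purpose for each scan. Besides confirmation it offers "Determine location of the catheter compared to the lesion" and a free 'Other'. The tool-in-lesion items are conditional on that answer:
- CBCT-FS: "If confirm tool-in-lesion purpose, can you confirm tool-in-lesion based on the CBCT-FS scan", answered yes, no or inconclusive.
- CBCT: "If confirm tool-in-lesion purpose, can you confirm tool-in-lesion (in all three orthogonal orientations) based on the CBCT scan", answered yes (in all three orientations), no, or 'Maybe' when scan quality is insufficient.

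For the centre-strike item, only the CBCT form has a third option: "Lesion is too small to define center-strike or off-center".

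**The concern.** The formula needs a yes or no from both scans in every pair, and the form does not deliver that. No section says whether pairs without two such readings are dropped, counted as failures or handled in some other way. The nearest guidance is the general rule in 8.3, which keeps a 'missing' category and bases percentages on the full total. It is written for subjects, but by analogy it points towards keeping unscored pairs in the denominator.

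The endpoint could then reflect why scans were made and how two questions were worded, as well as whether CBCT-FS shows the same thing as CBCT. A result held against 90%, and meant to inform a pivotal study (Section 8.2), would depend on a counting rule chosen after the readings are known.

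**Working it through.** **The plan's own figure.** The only sample-size arithmetic is 33 per-protocol subjects with 10% dropout: 33/0.90 = 36.7, rounded up to 37. This reproduces. It is not derived from the 90% threshold and is unaffected by this point.

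**Inputs.**
- Per-protocol subjects: 33 (8.2).
- CBCT-FS scans per procedure: 1 to 3 (Appendix VI, Table 7). This gives 33 × 1 = 33 to 33 × 3 = 99 pairs if every subject has at least one.
- Share of pairs without a usable yes/no reading: not in the documents, so a range is shown.

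**Step 1: ceiling from unscored pairs.** Let N be all pairs and U those not read yes or no on both scans. With perfect agreement in every scored pair, the formula gives at most (N − U)/N.

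| N | Largest U still at or above 90% | First U below 90% |
|---|---|---|
| 33 | 3: 30/33 = 90.9% | 4: 29/33 = 87.9% |
| 66 | 6: 60/66 = 90.9% | 7: 59/66 = 89.4% |
| 99 | 9: 90/99 = 90.9% | 10: 89/99 = 89.9% |

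Suppose each pair is independently unscored with probability 5%, 10% or 20% (assumed). The chance that a perfect CBCT-FS reaches 90% is then 0.92, 0.58 or 0.08 with 33 pairs, and 0.97, 0.46 or 0.003 with 99 pairs.

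**Step 2: wording.** Take a clear image with the tool in the lesion in two planes but not the third. On the CBCT form it is not a 'Yes', and 'Maybe' is reserved for poor scan quality, so it becomes a 'No'. The CBCT-FS form states no orientation condition, so the same view can be a 'Yes'. If a share d of scored pairs is discordant for this reason, accuracy is 1 − d: 90% at d = 10%, which still meets the threshold, and 85% at d = 15%.

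**Step 3: both together.** With unscored share u, accuracy is (1 − u)(1 − d). For u = d = 5%: 0.95 × 0.95 = 90.2%. For u = 10% and d = 5%: 0.90 × 0.95 = 85.5%.

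**Step 4: the open rule matters in both directions.** Take an invented set of 40 pairs: 28 agree, 2 disagree, 4 are CBCT-FS inconclusive and 6 are location scans.
- All pairs: 28/40 = 70%.
- Without location scans: 28/34 = 82%.
- Also without inconclusive readings: 28/30 = 93%.

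The same data pass or fail according to a rule the plan does not state.

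**The case against.** **Intended meaning.** The best reply is that 'pairs' was meant to cover confirmation scans only. Section 8.6 speaks of the tool-in-lesion confirmation scan, the Summary adds usefulness for guidance as a second basis of the endpoint, and Appendix II collects a usefulness score for every purpose. Location scans therefore have an outcome of their own. This is a plausible reading of intent, but no sentence restricts the denominator, and it leaves the CBCT 'Maybe' pairs and the difference in wording unresolved.

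**Wording.** A CBCT-FS 'Yes' against a CBCT that fails in one plane may be a real false positive, which the endpoint should detect. That is fair. The difficulty is that the form cannot separate such an error from a difference in criterion. Nothing shows that readers actually apply a looser standard to CBCT-FS, so the size of this effect is unknown.

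**Centre-strike.** A reader might infer that pairs scored too small on CBCT can never agree. Section 8.6 calls this an additional analysis of scans divided into two classes and gives no denominator that includes a third, so these pairs may already fall outside it. Only a clarification is needed.

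**Status of the study.** This is a single-centre feasibility study with no hypothesis test on accuracy. That limits the consequences, but the plan still attaches a sufficiency statement to 90%.

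**Conclusion.** The concern holds as a defect in the definition of a primary endpoint. Applied as written, the formula can put a CBCT-FS that agrees in every scored pair below 90%, once more than 10% of pairs are unscored or discordant through wording alone. Four of 33 pairs, or ten of 99, are enough. This rests on a literal reading of the denominator and on readers following the form literally.

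Two stronger conclusions are not supported. The first is that 90% will be missed: the documents give no share of unscored or wording-discordant pairs.

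The second is a specific ceiling. From the 2.25 and 2.93 acquisitions per procedure in Table 6, a reader might take 1.25 to 1.93 additional scans with one confirmation scan among them, and infer a maximum of 1/1.25 = 80% down to 1/1.93 = 52%. Those counts come from a cited cohort, whereas the study's own projection in Table 7 is 1 to 3 additional scans. Nothing limits a procedure to one confirmation scan: a negative reading, repositioning and a further confirmation scan give two scored pairs.

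**What to change.** In Sections 7.1.1 and 8.6:
- Define the evaluable pair as one where both scans were taken to confirm tool-in-lesion and the CBCT was read 'Yes' or 'No'.
- Keep CBCT-FS 'Inconclusive' in that denominator as non-agreement, so that the repair does not flatter the device.
- Report the numbers of excluded location-purpose, other-purpose and CBCT-'Maybe' pairs, and give accuracy over all pairs as a sensitivity analysis.
- Reconcile the procedure and the pair as the unit of the endpoint.
- State that pairs scored too small on CBCT are left out of the centre-strike analysis, or offer that option on both forms.

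In Appendix II, use the same orientation wording for both scans. The statistical need is that the criterion be common; its content is for the investigators.

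**Cost.** The denominator becomes smaller. The new denominator needs no new data, because purpose and answers are already recorded. The wording change affects only pairs collected afterwards; earlier pairs need a flag, or a re-reading where the image export in Section 9 permits it. Enrolment began in October 2023, so this changes a primary endpoint mid-study. It should go through the amendment route in Section 10, be fixed before the accuracy results are summarised, and show results before and after the change, as that section provides.

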7.1.1. Endpoints

The primary and secondary endpoints are based on the objectives (Section 6) and are described below.

Primary endpoints

The system usability will be assessed by using the System Usability Scale (SUS) ¹⁵. An average SUS of greater than 70 will indicate a good usability design of the AirWaze Software solution. The SUS will be measured per operator every 4 procedures.

Image-based tool-in-lesion confirmation accuracy of CBCT-FS is defined as the number of procedures where CBCT-FS scans were adequate to define tool-in-lesion compared to conventional CBCT scans (gold-standard). The image-based tool-in-lesion accuracy is defined as the sum of the number of tool-in-lesion in both the CBCT-FS and CBCT images (i.e. true positives), and the number of no tool-in-lesion confirmation in both the CBCT-FS and CBCT images (i.e. true negatives), divided by the total number of CBCT-FS and CBCT pairs. Image based tool-in-lesion confirmation accuracy of 90% will indicate that the CBCT-FS is postulated to be sufficient for navigation bronchoscopy.

IGT Systems	Feasibility Clinical Investigation Protocol AirWaze – easy and advanced tools for CBCT guided lung interventions	Doc ID: XCY607-130895 Rev: 04 Date: 2024-Jun-19 Page 20 of 56
-------------	--	--

Secondary endpoints

The secondary endpoints of this feasibility clinical investigation are:

- Semi-structured questionnaires to assess intuitiveness of AirWaze features for CBCT-guided biopsy of peripheral pulmonary nodules (Appendix III).
- Quantitative and qualitative assessment of the developed algorithms is assessed through a questionnaire (Appendix IV).
 - (a) Segmentation bronchial tree on pre-procedural CT.
 - (b) Elastic registration of the intraoperative CBCT scans with preprocedural CT scan.
 - (c) Automatic device detection on intraoperative CBCT scans.
- The quality of the interventional planning is defined by comparing the pre-procedural planned navigation trajectory compared to the actual navigation trajectory towards the first lesion (Appendix V).
- Confidence levels of pulmonologists are defined as a score (0-10) to examine the degree of confidence of specialists regarding: (i) the localization of the lesion and planned navigation trajectory; (ii) reaching the first pulmonary lesion based on the planning (Appendix V).

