The estimated radiation exposure of the AirWaze study is depicted in Table 7.

- Radiation exposure assumptions:
 - Verhoeven *et al.* has reported the radiation exposure of CBCT-guided navigation bronchoscopy for biopsy of PPNs. An average fluoroscopy time of 935 seconds was used for real-time navigation and sampling guidance. The average total DAP for these 935 seconds was 2.2 Gy·cm².
 - It is expected that the implementation of AirWaze CBCT-FS will reduce the fluoroscopy time and thus the overall DAP. This benefit of an expected reduction in fluoroscopy time is not considered in the calculations as depicted in Table 7.
- AirWaze and CBCT-FS are implemented for testing the clinical and technical feasibility. The first performed scan during a procedure is a conventional CBCT. In case additional scans are required, a CBCT-FS scan is performed on top of the conventional imaging protocol. A comparison between the additional CBCT and CBCT-FS is then made. The DAP per CBCT-FS acquisition is less than 1.45 Gy·cm² based on preclinical studies.

IGT Systems	Feasibility Clinical Investigation Protocol AirWaze – easy and advanced tools for CBCT guided lung interventions	Doc ID: XCY607-130895 Rev: 04 Date: 2024-Jun-19 Page 54 of 56
-------------	--	--

Table 7. Expected estimated radiation exposure during this Feasibility Clinical Investigation

	Low Dose Fluoroscopy		CBCT			CBCT-FS*		Total DAP (Gy·cm ²)
	DAP (Gy·cm ²)	Time (s)	Protocol	DAP (Gy·cm ²) / acq.	Acqs.	DAP (Gy·cm ²) / acq.	Acquisitions	
CBCT-NB w/o AirWaze	2.2	935	Normal dose	11.55	1	-	-	20.8-37.8
			Low dose	8.02	1-3			
Study (n=22)	2.2	935	Normal dose	11.55	1	-	-	22.3-42.2
			Low dose	8.02	1-3	1.45	1-3	

* The number of CBCT-FS scans are expected to be equal to the number of additional low dose CBCT scans performed (=total number of CBCT minus one).

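### The 90% mark for CBCT-FS is a bare agreement rate with no interval and no planned false-confirmation figure, so passing it is a weak go-signal

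*Combined protocol and SAP*

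**What the plan says.** The accuracy endpoint is set out in nearly the same words in Sections 7.1.1 and 8.6.

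- **Lead-in sentence (8.6).** "Image-based tool-in-lesion confirmation accuracy of CBCT-FS is defined as the number of procedures where CBCT-FS scans were adequate to define tool-in-lesion". This counts procedures and has no denominator.
- **Formula (8.6).** "The accuracy is defined as the sum of the number of tool-in-lesion in both CBCT-FS and CBCT", plus the pairs in which both scans show no tool in lesion, "divided by the total number of CBCT-FS and CBCT pairs". This is raw agreement per scan pair.
- **Pass mark (8.6).** "Image based tool-in-lesion confirmation accuracy of 90% will indicate that the CBCT-FS is postulated to be sufficient for navigation bronchoscopy".
- **Analysis (8.6).** "The results will be analyzed by calculating the overall accuracy of the CBCT-FS for tool-in-lesion confirmation". The one further analysis, centre against off-centre strike, is restricted to scans that confirmed tool-in-lesion.
- **General rules (8.3).** A 95% CI is listed with the mean. For categorical results, "Categorical data will be summarized as the number and percentage of subjects in each category".
- **Number of pairs (Appendix VI, Table 7).** 1 to 3 CBCT-FS acquisitions per procedure; "The number of CBCT-FS scans are expected to be equal to the number of additional low dose CBCT scans performed".
- **Reads (Appendix II).** CBCT-FS can be read as yes, no or inconclusive. CBCT can be read as yes, no or maybe.
- **Sample size (8.2).** 37 patients, 33 of them per protocol, justified by expert expectation.

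**The concern.** Raw agreement adds true positives and true negatives, so it is dominated by whichever state is more common. If most confirmation scans are made when the tool is already in the lesion, CBCT-FS can agree with CBCT nine times in ten and still do poorly on the scans where CBCT shows that the tool missed. A later decision to rely on CBCT-FS needs that second rate, and no planned summary shows it.

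The mark is also applied to the observed percentage alone. Nothing in 8.6 attaches a confidence limit to it, allows for several pairs from one patient, or says how an inconclusive or maybe read is counted.

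Section 8.2 says the results will feed the design of a pivotal study, and Appendix IV names replacement of CBCT by CBCT-FS as the desired future use. A pass that does not separate good performance from a favourable case mix would be poor guidance for both.

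**Working it through.** **Inputs from the documents.** Mark 90%, read here as at least 90% observed; 33 per-protocol patients; 1 to 3 pairs per procedure. That gives 33 to 99 pairs if every procedure contributes, and fewer if some scans were not made to confirm tool-in-lesion.

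**Assumptions.** The share of failed placements and the intra-patient correlation (ICC) are not in the documents, so both are shown as ranges.

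**The plan's own figure.** 33/0.9 = 36.7, rounded up to 37, which matches. No power or precision calculation accompanies the 90% mark.

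**1. What agreement hides.** With q the share of pairs that CBCT reads as not in lesion,

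accuracy = sensitivity × (1 − q) + specificity × q.

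Take sensitivity 100% and specificity 50%, so accuracy = 1 − 0.5q.

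| q | Expected accuracy | Chance of passing, 33 pairs | Chance of passing, 99 independent pairs |
|---|---|---|---|
| 10% | 95% | 92% | 97% |
| 20% | 90% | 58% | 46% |
| 30% | 85% | 25% | 6% |
| 40% | 80% | 8% | 0.3% |
| 50% | 75% | 2% | 0.01% |

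Expected accuracy stays at or above 90% only while q is at most 20%. In counts, 27 true positives, 3 true negatives and 3 false positives give 30/33 = 90.9%, a pass, with specificity 3/6 = 50% (exact 95% CI 12% to 88%). With 30 positives and 3 negatives, reading every scan as in lesion also passes at 30/33, with specificity zero.

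**2. What the point estimate allows.** The mark needs 30 of 33 pairs (exact 95% CI 75.7% to 98.1%) or 90 of 99 (83.4% to 95.8%). Exact binomial chance of passing with independent pairs:

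| True accuracy | 33 pairs | 66 pairs | 99 pairs |
|---|---|---|---|
| 80% | 8.1% | 1.4% | 0.3% |
| 85% | 25.0% | 11.7% | 6.0% |

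**3. Clustering.** For 33 patients with 3 pairs each, a beta-binomial simulation with ICC 0.2 to 0.5 gives a chance of passing of about 10% to 14% at true accuracy 85%, and 1% to 3% at 80%. For precision at 90% accuracy, the half-width that ignores clustering is 1.96 × √(0.9 × 0.1/99) = 5.9 points. The design effect is 1 + (3 − 1) × ICC:

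- ICC 0.1: 5.9 × √1.2 = 6.5 points.
- ICC 0.6: 5.9 × √2.2 = 8.8 points.

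**4. Inconclusive reads.** The numerator takes only yes/yes and no/no pairs. Taken literally, the denominator keeps every pair, but 8.6 does not say whether a pair with an inconclusive or maybe read is one of them. Dropping those pairs after the fact would raise the percentage.

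**The case against.** The strongest reply is that this is a feasibility study. The wording is tentative, there is no hypothesis test, and CBCT remains the reference scan throughout, with CBCT-FS acquired in addition to it. That stands, and it limits the harm to the planning of the next study.

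Four stronger readings are tempting, and the documents do not support them.

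- **That false confirmations will be lost.** Section 8.3 lists all data, and Appendix II records both reads and whether CBCT changed the plan. The count is recoverable; it is just not a pre-specified summary.
- **That the endpoint has two rival units.** The sentence "defined as the number of procedures where CBCT-FS scans were adequate to define tool-in-lesion" has no denominator and cannot give a percentage. Only the pair formula can be computed. A reader could construct a reversal: 9 discordant pairs of 99, in 9 different procedures, give 90/99 = 90.9% by pair but 24/33 = 72.7% if every pair in a procedure must agree. That second rule is not in the plan. The problem is loose wording.
- **That a pass is likely at true accuracy well below 90%.** This holds only near 33 pairs. At 99 independent pairs the risk is 6% at 85% and 0.3% at 80%.
- **That half of the failed placements will be missed.** The calculation shows that the rule permits this when failed placements are few. Nothing in the documents says that CBCT-FS performs so, or how common failed placements are.

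It may also be said that 8.3 promises a 95% CI for all results. It lists one with the mean and gives number and percentage of subjects for categorical data. Even on the generous reading, no limit enters the 90% rule, and a per-subject summary does not fit a per-pair endpoint.

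**Conclusion.** The concern holds as a should-fix. The 90% mark is a point estimate of agreement, with no interval tied to it and no planned figure for sensitivity, specificity or false confirmations.

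It can be met with half of the failed placements missed, provided that these are at most about 20% of pairs (assumption) and sensitivity is near 100%. The chance of passing at true accuracy 85% runs from 25% with 33 independent pairs to 6% with 99, or about 10% to 14% with 99 pairs and an assumed ICC of 0.2 to 0.5. More pairs reduce that risk but leave the specificity question open: with failed placements at 10% of pairs and specificity 50%, 99 pairs pass more often than 33.

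The per-procedure wording and the silence on inconclusive reads are smaller defects in the same definition. The consequence is a weak go-signal for the pivotal study. A reader should not infer a false confirmatory claim, since the plan makes none.

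**What to change.** In Sections 7.1.1 and 8.6:

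1. State that the unit is the CBCT-FS/CBCT pair made for tool-in-lesion confirmation, and reword the per-procedure sentence to match.
2. Pre-specify the full cross-table of CBCT-FS reads (yes, no, inconclusive) by CBCT reads (yes, no, maybe).
3. Count an inconclusive CBCT-FS read as not concordant in the main accuracy figure. Report pairs with a CBCT maybe separately, as having no reference result. Add a sensitivity analysis that excludes inconclusive reads.
4. Report accuracy, sensitivity, specificity and the false-confirmation count, with 95% CIs that allow for several pairs per patient. A Wilson or Clopper-Pearson interval on a sample size divided by the design effect is suitable. It still works at 100% agreement, where a patient-level bootstrap has zero width, but the ICC cannot be estimated there, so fix a fallback value in advance.
5. Put the lower limit and the specificity beside any statement about 90%, and make no sufficiency statement on overall accuracy alone. Requiring the lower limit itself to reach 90% is not the remedy: with 33 pairs the exact limit falls short even at 33/33.

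**Cost.** No new data are needed, because Appendix II already collects the reads. The result will read less favourably, and specificity will be imprecise if few CBCT scans are negative. Enrolment began in October 2023 (7.3.2), and Section 10 does not treat changes related to endpoints as non-significant, so the rewording may need a protocol amendment with ethics committee approval.
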